##### 4.4.1 Major Permitted Therapies for NMO

##### **Permitted Medication/Therapy During the Double-Blind Period**

###### 1. Baseline treatment

One of the drugs listed below is required as monotherapy for baseline treatment at baseline. A dose must not exceed the dose defined below and a stable dose must be maintained. Dose decrease is permitted only for safety reasons. Dose increase or change of baseline treatment is not permitted.

- Azathioprine\*: 3 mg/kg/day
- Mycophenolate mofetil\*: 3000 mg/day
- Oral corticosteroids: 15 mg/day (prednisolone equivalent)

\* Combination with oral corticosteroids (15 mg/day [prednisolone equivalent]) is permitted in patients aged 12 to 17 years at the time of informed consent.

2. Rescue therapy for clinical relapse (leads to end of the double-blind period); pulse IV corticosteroids, intravenous immunoglobulin (IVIG), and/or apheresis (including plasma exchange and plasmapheresis).

Rescue therapy should proceed at the discretion of the treating Investigator after the examining assessor has completed EDSS/FSS assessment at extra visit at relapsing (except in case of emergency when urgent treatment is required before the patient can undergo this assessment).

3. Pain medications (including but not limited to pregabalin, gabapentin, carbamazepine, clonazepam, duloxetine, tramadol/acetaminophen).

Starting of pain medications is permitted, however the dose should be stable during the double-blind period. In case pain control is insufficient, dose increase or change of pain medication is permitted. Dose decrease and temporary treatment suspension are permitted for only safety reasons.

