#### **6.5.1 Primary Efficacy Endpoint**

The primary efficacy endpoint is TFR based on protocol-defined relapses confirmed by the CEC with EDSS/FSS assessment performed by the examining assessor within 7 days after relapse symptoms were reported to site by the patient. TFR is defined as the time from the date of the randomization until the first occurrence of relapse throughout the double-blind period. The time point of relapse onset is defined as the time at which the patient experiences any new or worsening neurological NMO representing clinical relapse(s). Events which are judged by the CEC to meet the protocol-defined relapse will be included in the primary analysis of the primary endpoint if EDSS/FSS is assessed by the examining assessor within seven days after

the patient reports the symptoms to the site. For patients who have not relapsed, not switched baseline treatment or not increased baseline treatment at the time of analysis, the TFR will be censored on the date when total number of protocol-defined relapses judged by CEC reaches 26. For patients who have switched baseline treatment or increased baseline treatment, the TFR will be censored on the date of switching or increasing the baseline treatment. For patients who have received rescue therapy without experiencing a protocol-defined relapse for which the EDSS/FSS assessment was not performed within seven days after the patient reports the symptoms to the site, the TFR will be censored on the date of receiving rescue therapy.

The primary analysis of the study is to test the equality of the TFR distribution in the satralizumab (SA237) +baseline treatment (satralizumab [SA237]) and Placebo +baseline treatment (placebo) arms:

$$H_0: TFR_{SA237} = TFR_{\text{placebo}} \text{ versus } H_1: TFR_{SA237} \neq TFR_{\text{placebo}}$$

A stratified two-sided log-rank test using strata of baseline ARR (one vs. more than one) and geographical region will be used.

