## **6.9 HANDLING MISSING DATA**

For TFR, patients who have not relapsed, not switched baseline treatment or not increased baseline treatment dose at the time of analysis, the TFR will be censored on the date when total number of protocol-defined relapses judged by CEC reaches 26. For patients who have switched baseline treatment or increased baseline treatment dose, the TFR will be censored on the date of switching the baseline treatment or increasing the baseline treatment dose. For patients who have received rescue therapy without experiencing a protocol-defined relapse for which the EDSS/FSS assessment was not performed within seven days after the patient reports the symptoms to the site, the TFR will be censored on the date of receiving rescue therapy.

For key secondary endpoints, missing data at Week 24 in the double blind period will be imputed by a BOCF and for the purpose to assess the robustness of the imputation method, we will also conduct hot-deck imputation as sensitivity analysis.

For secondary continuous endpoints, a MMRM analysis incorporating data in double-blind phase will be used to utilize data collected over time with consideration of the variance-covariance matrix of the repeated measures. This method allows a general unstructured variance-covariance matrix and will include data from patients with incomplete data from some scheduled time points.

For the FACIT fatigue questionnaire, if there are less than 7 responses recorded, then the total fatigue score will be considered missing. If there are 7 or more responses recorded, then the total fatigue score for that questionnaire will be calculated as the average of the non-missing scores multiplied by 13.

Detailed methods for handling of missing data will be mentioned in the SAP.

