5.10.2 Primary Efficacy Variable

The primary efficacy analyses will be based on the ITT population. Supportive evaluations will be performed using the PPS population.

The primary efficacy endpoint is TFR based on protocol-defined relapses confirmed by the CEC with EDSS/FSS assessment performed by the examining assessor within 7 days after relapse symptoms were reported to site by the subject. TFR is defined as the time from the date of the randomization until the first occurrence of relapse throughout the study. Time point of relapse onset is defined as time at which the subject experiences any new or worsening neurological NMO representing clinical relapse(s) which is later confirmed by the CEC as protocol-defined.

Censor is defined as the earliest day of 1) the end of double blind period for efficacy analysis, 2) switching or increasing the baseline treatment (for details on the identification of the switch and increase in baseline therapy see appendix 7.4), or 3) receiving rescue therapy for clinical relapse.

The primary analysis of the study is to test the equality of the TFR distribution based on protocol-defined relapse in the SA237 + baseline treatment (SA237) and Placebo + baseline treatment (placebo) arms:

$$H_0: TFR_{SA237} = TFR_{\text{placebo}} \text{ versus } H_1: TFR_{SA237} \neq TFR_{\text{placebo}}$$

A stratified two-sided log-rank test using strata of baseline ARR (one vs. more than one) and geographical region (Asia and EU/Other) will be used.

The Kaplan-Meier method will be used to estimate the TFR based on protocol-defined relapses distribution for each treatment group. The Kaplan-Meier curve will provide a visual description of the differences across treatment groups. In addition, estimates of the treatment effect will be expressed as hazard ratio and 95% CIs using a stratified (baseline ARR and geographical region) Cox proportional-hazards model (Exact method will be used for tie data). Treatment by covariate interactions will be assessed by including the pairwise interaction terms in the Cox proportional-hazards model.

The following summary tables, figures and analysis will be provided for the ITT and PPS:

- A summary table of Kaplan-Meier estimate of TFR (protocol-defined relapse) will be presented by treatment group.
- A figure of Kaplan-Meier estimate of TFR (protocol-defined relapse) will be presented by treatment group.
- Analysis of TFR (protocol-defined relapse) will be performed using the stratified log-rank test.

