- Analysis of TFR (protocol-defined relapse) will be performed using the stratified Cox regression.

The subgroup forest plot of HR of TFR (protocol-defined relapse) will be presented by the defined variables in Section 5.5.

Additionally, summary tables of sensitivity analysis of TFR (clinical relapse), TFR (treated clinical relapse), TFR (treated clinical relapse: optic neuritis) , protocol-defined relapse

based on CEC adjudication (regardless of assessment limit of 7 days) and protocol-defined relapse based on EDSS/FSS increase relative to baseline will be conducted for ITT as follows. All relapses reported by investigators will be handled as events for TFR (clinical relapse). Relapses treated with rescue therapy will be handled as events in addition to protocol-defined relapses for TFR (treated clinical relapse). Relapses treated with rescue therapy and judged optic neuritis by investigator will be handled as events in addition to protocol-defined relapses for TFR (treated clinical relapse: optic neuritis). Optic neuritis will be identified via relapse assessment form before data base lock (for details see appendix 7.4).. The same censoring rules as for the primary endpoint will be applied, except for the specific event of interest.

- A summary table of Kaplan-Meier estimate of TFR (clinical relapse) will be presented by treatment arm.
- A summary table of Kaplan-Meier estimate of TFR (treated clinical relapse) will be presented by treatment arm.
- A summary table of Kaplan-Meier estimate of TFR (treated clinical relapse: optic neuritis) will be presented by treatment arm.
- A summary table of Kaplan-Meier estimate of TFR (protocol-defined relapse based on CEC adjudication (regardless of assessment limit of 7 days)) will be presented by treatment arm.
- A summary table of Kaplan-Meier estimate of TFR (protocol-defined relapse based on EDSS/FSS increase relative to baseline) will be presented by treatment arm.
- A figure of Kaplan-Meier estimate of TFR (clinical relapse) will be presented by treatment group.
- A figure of Kaplan-Meier estimate of TFR (treated clinical relapse) will be presented by treatment group.
- A figure of Kaplan-Meier estimate of TFR (treated clinical relapse: optic neuritis) will be presented by treatment group.
- Analysis of TFR (clinical relapse) will be performed using the stratified log-rank test.
- Analysis of TFR (treated clinical relapse) will be performed using the stratified log-rank test.

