7.4 Step to identify the Day of baseline treatment increase/change:

[Step]

1. Identify “Relapse prevention therapy used at BL (i.e. Drug A)”.
2. Identify “Relapse prevention therapy* newly used from BL by the potential censored Day** other than the Day of increase/change of BL treatment (i.e. Drug B)”.
 - ✓ End if there is no Drug B.
3. Scientifically/medically evaluate if any of following information of Drug A are different from those of Drug B:
 - i. Dose regimen
 - ii. Drug name
 - ✓ End if not different.
 - ✓ If different, the earliest start Day of Drug B is the Day of dose increase/change of baseline treatment.

*; Including immunosuppressants and corticosteroids which were not used for relapse prevention (i.e. the indication is AE or Medical History etc). For them, route and duration of administration etc. will also be considered in step No.3 (e.g. temporal local administration will not be considered as increase/change of Drug A).

**; Including following days;

- a. 1st Day of rescue therapy started in the double-blind period for this patient (if any)
- b. The relapse onset Day of the event*** for this patient (if any)
- c. Clinical cut-off Day (CCOD): the relapse onset day of the event*** with the 26th earliest onset date
- d. Day of discontinuation from the double-blind period for this patient (e.g. Day of WD visit, Day of consent withdrawal) (if any)

***; the relapse adjudicated as protocol-defined relapse by Clinical Endpoint Committee (CEC) and EDSS/FSS assessed within 7 days from the date when the patient first reported symptoms to the site.

[Note]

- Day 1 = Baseline in the double blind period
- There may be more than one Drug B.
- Drug A must meet both of followings:
 - ✓ “Day of medication started” ≤ 1
 - ✓ “Day of medication stop” ≥ 1
- Drug B must meet both of followings:
 - ✓ “Day of medication started” ≥ 1
 - ✓ “Day of medication started” $<$ “potential censored Day***”

7.5 Procedure to identify the clinical relapse of optic neuritis occurred in the double-blind period:

The clinical relapse of optic neuritis occurred in the double-blind period of SA-307JG study will be identified by satisfying with either or both of followings. The Relapse Assessment Form (RAF) completed by study sites will be used for the identification.

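### SAP appendix 7.4 sets the baseline-treatment censoring date on any dose difference, so a permitted safety decrease can be censored although the governing rule censors only a switch or an increase

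*SAP*

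**What the plan says.** The governing rule names a direction. Protocol 6.5.1: "For patients who have switched baseline treatment or increased baseline treatment, the TFR will be censored on the date of switching"; the date of an increase is treated likewise. Protocol 6.9 repeats it: "the TFR will be censored on the date of switching the baseline treatment or increasing the baseline treatment dose". SAP 5.10.2 lists the same two triggers and delegates the date: "for details on the identification of the switch and increase in baseline therapy see appendix 7.4".

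Protocol 4.4.1 keeps a decrease apart from these triggers for the double-blind period: "Dose decrease is permitted only for safety reasons. Dose increase or change of baseline treatment is not permitted".

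In SAP appendix 7.4, Drug A is the relapse-prevention therapy in use at baseline. Drug B is relapse-prevention therapy newly used after baseline and before the patient's other potential censoring days. Step 3 reads: "Scientifically/medically evaluate if any of following information of Drug A are different from those of Drug B", the items being dose regimen and drug name. If they differ, "If different, the earliest start Day of Drug B is the Day of dose increase/change of baseline treatment".

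The same appendix defines the clinical cut-off as the onset day of the qualifying relapse "with the 26th earliest onset date". For the TFR sensitivity analyses, SAP 5.10.2 states: "The same censoring rules as for the primary endpoint will be applied, except for the specific event of interest".

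**The concern.** A lower dose is a different dose regimen. Step 3 therefore returns a date of increase or change for a dose that was reduced, and SAP 5.10.2 uses that date to censor the primary endpoint. The patient affected has followed the protocol and remains in the double-blind period.

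Three consequences follow.

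- **Lost events.** A relapse after the decrease drops out of an analysis sized on 26 events.
- **No replacement under appendix 7.4.** The cut-off counts CEC-adjudicated relapses with EDSS/FSS assessed within 7 days. It does not exclude patients already censored for baseline treatment. A relapse could count towards the cut-off and still not be an event in the analysis.
- **Hidden from the sensitivity analyses of TFR.** These use the same censoring rules.

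Decreases made for safety may also be related to treatment or prognosis, so the censoring could be informative. The documents do not show that it is.

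**Working it through.** **1. The texts side by side**

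| Source | What triggers censoring | Direction tested? |
|---|---|---|
| Protocol 6.5.1 | Switch or increase | Yes |
| Protocol 6.9 | Switch or dose increase | Yes |
| SAP 5.10.2 | Switch or increase, date from 7.4 | Yes |
| SAP 7.4 step 3 | Dose regimen or drug name differs | No |

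The date conditions and footnotes of 7.4 add no test of higher versus lower. The one written exemption, for temporary local administration, concerns drugs not given for relapse prevention. For a same-drug increase to be found at all, a changed dose must appear as a Drug B record. The same convention would pick up a decrease.

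**2. The plan's own figure**

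Inputs from Protocol 6.2: HR 0.335, two-sided 5%, 80% power, 1:1 allocation. Schoenfeld: d = 4(1.96 + 0.8416)² / (ln 0.335)² = 26.25, which agrees with the stated 26 (27 if rounded up).

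**3. Power with fewer events**

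Power = Φ(√(d/4) × |ln 0.335| − 1.96), with |ln 0.335| = 1.0936.

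| d | √(d/4) × 1.0936 | Power |
|---|---|---|
| 26 | 2.788 | 79.6% |
| 25 | 2.734 | 78.1% |
| 24 | 2.679 | 76.4% |
| 23 | 2.622 | 74.6% |

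**4. Events lost, for an assumed share of patients**

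From Protocol 6.2: 35 per arm; placebo hazard 0.4184 per year; satralizumab hazard 0.4184 × 0.335 = 0.1402; dropout hazard −ln(0.9)/2 = 0.0527; one year of accrual plus 1.5 years. Uniform accrual is assumed, so follow-up is uniform on 1.5 to 2.5 years.

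The probability of an event by time t is h/(h + 0.0527) × (1 − exp(−(h + 0.0527)t)).

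- Over full follow-up: 18.86 + 8.11 = 26.97 events.
- By month 6: 35 × (0.1864 + 0.0668) = 8.86, leaving 18.11 later.
- By month 12: 35 × (0.3337 + 0.1275) = 16.14, leaving 10.83 later.

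Loss = share × later events × 26/26.97. The share is assumed equal in both arms, with the hazard unchanged by the decrease:

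| Share with a decrease | Lost, month 6 | Lost, month 12 |
|---|---|---|
| 5% | 0.87 | 0.52 |
| 10% | 1.75 | 1.04 |
| 15% | 2.62 | 1.57 |

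As an alternative, decreases were spread over time. If 5%, 10%, 20% or 30% of patients have one by two years, 25.4, 24.8, 23.6 or 22.3 of 26 events remain, with power 78.7%, 77.8%, 75.7% or 73.4%.

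**5. Effect on the hazard ratio**

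Large-sample Cox runs used 1,000,000 patients per arm and a decrease at month 6.

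- Equal shares, hazard unchanged: HR 0.334 to 0.336 with or without the censoring.
- Equal shares, hazard doubled after the decrease: a shift of at most 0.007.
- Unequal shares, hazard doubled: 15% satralizumab/5% placebo moves the HR from 0.357 uncensored to 0.336 censored; 5%/15% moves it from 0.320 to 0.335.

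The shift can go either way.

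**The case against.** The governing rule is stated three times and is directional. On this view 7.4 is only a look-up procedure whose heading echoes the prohibited pair in Protocol 4.4.1. Step 3 calls for scientific and medical evaluation, so a sensible evaluator would pass over a decrease. A reduced dose reaches step 3 only if it is entered as a new record and read as newly used therapy, which no document states. No rate of decreases is given. Protocol 6.2 provides a blinded review that may add patients or extend the double-blind period. The annualized relapse rate analysis states no baseline-treatment censoring, and by-subject listings would let affected patients be found.

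Much of this stands. Censoring a decrease is not automatic, its frequency is unknown, and the blinded review could make up lost events. It does not remove the conflict. The evaluator is asked only whether the records differ, and the consequence of a difference is fixed. If evaluators apply an unwritten exemption for decreases, the censoring rule is not fully pre-specified. Listings may show what happened but do not change the primary analysis.

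**Conclusion.** The concern holds. As written, step 3 of SAP appendix 7.4 can produce a censoring date that Protocol 6.5.1, Protocol 6.9 and SAP 5.10.2 do not allow. It should be fixed. Confidence is medium, because the effect depends on two things the documents leave open: whether a reduced dose is recorded as a new entry, and how often decreases occur before a patient's relapse or other censoring day.

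The size cannot be derived from the documents and may be nil. Under the assumed 5% to 15% of patients, the loss is about 0.5 to 2.6 of 26 events. A loss of one to three whole events costs 1.5 to 5.0 points of power (79.6% to 78.1%, and to 74.6%). With equal shares the hazard ratio barely moves. With unequal shares and a changed hazard it can move either way, so no direction of bias is claimed.

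**What to change.** Make step 3 directional. The day is set when Drug B is a different or added drug, or the same drug at a higher dose than Drug A. State that a dose decrease alone is not a censoring event. Keep step 2's definition of Drug B and its footnote on immunosuppressants and corticosteroids given for other indications, so that existing censoring is not narrowed by accident.

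It would also help to state which reference dose defines an increase when a reduced dose is later raised again; the documents do not say. Protocol 1.3 reports that the double-blind period is complete, so the sponsor should state how any decreases were classified in the analysis.

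The cost is two sentences in the appendix and the matching derivation of the censoring date. The 26-event design is unchanged. This concerns the analysis rule only and takes no position on dosing.

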7.6 Rule for summary of titer for anti AQP4 antibody status

Titer for anti AQP4 antibody status except screening visit will be replaced by following rule. This rule will apply to throughout TFL.

- If value is "<16", value will be replaced as 4.
- If titer is character (eg. ">16384", ">65536" except "<16") or titer is numeric more than 16384 (eg. "65536", "262144"), value will be replaced as 65536.

7.7 SAS Codes:

Log-rank test:

```
proc lifetest data=final;  
  
    time DURATION*STATUS (0);  
  
    strata ARR REGEON / group=TREATMENT;  
  
    ods output test=_logrank;  
  
run;
```

Cox Regression Model:

```
proc phreg data=final;  
  
    class TREATMENT/descending;  
  
    Model DURATION*STATUS(0)=TREATMENT / ties=exact rl;  
  
    strata ARR REGION;  
  
    ods output parameterEstimates=est;  
  
run;
```

Mixed effect Model Repeat Measurement (MMRM)

```
proc mixed data=VAS method=REML;  
  
    class REGION TREATMENT VISIT USUBJIDARR;  
  
    model CHG = BASE TREATMENT REGION VISIT ARR  
    TREATMENT*VISIT/ddfm=KR;  
  
    repeated VISIT / type=un subject = USUBJID;  
  
    lsmeans TREATMENT*VISIT / pdiff cl;
```

```
ods output lsmeans = lsm; * contains the adjusted means;  
ods output diffs = dif; * contains treatment differences;  
  
run;
```

ANCOVA:

```
proc mixed data=;  
  
class TREATMENT ARR REGION;  
  
model CHG_BL=TREATMENT BASELINE ARR REGION;  
  
lsmeans TREATMENT / pdiff cl;  
  
run;
```
